4.2.4 REPEATED SCREENINGS

In some circumstances a repeated screening may need to be scheduled. Examples include, but are not limited to:

1. Incomplete information available at time of screening to determine eligibility (e.g. current lens brands worn, history from current eye care practitioner etc.)
2. Study procedures unable to be completed in time scheduled for visit;
3. Study products not available at the time of the screening visit;
4. A transient health condition which may affect the eye(s) (e.g. a common cold, active allergies, fatigue etc.);
5. The short term use of medications (e.g. antibiotics, antihistamines etc.);
6. Reassessment of baseline ocular conditions (e.g. corneal and/or conjunctival staining, scars etc.).

The maximum total number of screenings permitted will be 3 (i.e. a maximum of two rescreen visits is permitted).

4.3 STUDY MATERIALS

4.3.1 LENSES

All participants will have worn, or be fit with an optimized prescription of Proclear 1 Day for at least 7 days prior to being fit and dispensed with Clariti 1 Day. Details of both lens types used in this study are listed in Table 1.

Table 1: Lens characteristics

Lens	Clariti 1 Day (Coopervision, Inc.)	Proclear 1 Day (Coopervision, Inc.)
Material	Somofilcon A	Omafilcon A
HC licence #	81009	60845
Water content (%)	56	60
Dk/t (barrer/cm)	86	36.6
Sphere power (D)	+6.00 to -10.00D	+8.00 to - 12.00
Base curve (mm)	8.6	8.7
Diameter	14.1	14.2

4.3.2 LENS CARE SYSTEM

No lens care systems are required as this study involves the use of daily disposable contact lenses.

4.3.3 REWETTING DROPS

Participants will not be encouraged to use rewetting drops; however, those who habitually used rewetting drops will be allowed to continue using their normal drops. Rewetting drop use will be recorded at the follow-up visit. In the event of an adverse event, rewetting drops may be given to participants.

4.3.4 ORDERING CONSUMABLES

Clariti 1 Day will be supplied by the sponsor. If they have difficulty sourcing product in good time then lenses may instead be purchased by the CCLR through a commercial route. Proclear 1 Day may be sourced from the sponsor or through a commercial route, depending on delivery times and urgency of need.

4.3.5 DISPOSING OF CONSUMABLES

This study provides contact lenses to participants for use during the study. Participants will be instructed to dispose of worn lenses daily, but retain the foils of all used lens packs and return them together with any unworn lenses, at their next study visit. Lenses worn for the scheduled visits will be collected from the participants and they will be disposed according to UW guidelines. Worn lenses associated with adverse events may be retained either at the CCLR or returned to CooperVision. Typical analysis in these cases relates to inspection for damage and/ or bacterial contamination. Upon completion of the study, all worn lenses will be destroyed, unless otherwise directed by the study Sponsor.

4.3.6 PRODUCT ACCOUNTABILITY

Accountability logs will be kept to include the number of lenses received, dispensed, unused and returned to sponsor (where relevant). All products dispensed to participants will be recorded in the study binder.

4.4 SCHEDULED AND UNSCHEDULED VISITS

4.4.1 STUDY VISITS

This study has 4 to 6 scheduled study visits (including the screening visit), depending on the participant's habitual lens type and lens power needs (Table 2). The total time commitment for scheduled visits is expected to be 2.75 to 3.75 hours.

Table 2: Summary of visits

Visit code	Visit schedule	Visit Description	Duration (hrs)
1		Screening and establish optimum power of Proclear 1 Day; fit Proclear 1 Day (if applicable) and Clariti 1 Day.	1 (1.25 if fitting both lenses)
1A*		Dispense new or modified power Proclear 1 Day**	0.5
1B***	≥7 days after V1A or concurrent to V1	Review Proclear 1 Day and baseline data collection	0.5
2		Dispense Clariti 1 Day****	0.5
3	7-12 days after V2	Review Clariti 1 Day	1
4		Study exit	0.25

*Note: Visit 1A is only necessary if a change in Proclear 1 Day lens power is required, or if a fit with Proclear 1 Day is required for adaptation

**Note: Visit 1A can be concurrent to Visit 1

***Note: Visit 1B can also be concurrent to Visit 1 if a habitual Proclear 1 Day wearer does not require a change in lens power

****Note: For habitual Proclear 1 Day wearers that do not require a change in lens power, Visit 2 can be concurrent to Visit 1

4.4.1.1 VISIT 1: SCREENING AND ESTABLISH OPTIMUM POWER OF PROCLEAR 1 DAY

Participants will attend a screening visit during which informed consent will be obtained and the investigator will determine participant eligibility using the inclusion and exclusion criteria. Participants will be assigned a study ID number when they sign the informed consent document, and before their eligibility for the study has been confirmed. Ineligible participants will be discontinued from the study. Depending on the participant's habitual lens type, participants may follow the following procedures and visits outlined (illustrated in Figure 2).

[figure not shown]

Figure 2: Flow chart for visits depending on habitual lens type (P1D = Proclear 1 Day; C1D = Clariti 1 Day).

*Following Visit 1A, participant also completes Visit 1B before proceeding the Visit 2

Habitual Proclear 1 Day wearers:

Participants that habitually wear Proclear 1 Day lenses will attend Visit 1 wearing their own Proclear 1 Day lenses. Participant demographics, including their contact lens history, wear schedule, health and medication will be recorded. Monocular and binocular distance visual acuity (high contrast, high illumination) and an over-refraction will be conducted with the participant's habitual Proclear 1 Day lenses in situ. The lenses will be assessed for fit acceptance.

If the power of the participant's habitual Proclear 1 Day lenses is confirmed to be optimal, the following procedures will be conducted:

- Visit 1B will be completed immediately (specifically: fit assessment and collection of subjective ratings for Proclear 1 Day)
- Remove contact lenses
- Visual acuity with habitual spectacles (high contrast, high illumination)

- Automated refraction and keratometry
- Subjective sphero-cylindrical and best-vision sphere refraction plus distance visual acuity (high contrast, high illumination), monocular and binocular
- Ocular health assessment
- The participant will be fit with Clariti 1 Day
- Investigator refit ratings
- Eligibility will be confirmed and the participant continues to Visit 2

If the power of the participant's habitual Proclear 1 Day lenses requires amendment, the following procedures will be conducted:

- Remove contact lenses
- Visual acuity with habitual spectacles (high contrast, high illumination)
- Automated refraction and keratometry
- Subjective sphero-cylindrical and best-vision sphere refraction plus distance visual acuity (high contrast, high illumination), monocular and binocular
- An ocular health assessment will be conducted
- The participant will be fit with Clariti 1 Day
- Investigator refit ratings
- Eligibility will be confirmed and the participant continues to Visit 1A

Habitual wearers of other lenses:

Participants that habitually wear other soft lens types will be asked to attend Visit 1 wearing their glasses. Participant demographics, including their contact lens history, wear schedule, health and medication will be recorded. The following procedures will then be conducted:

- Visual acuity with habitual spectacles (high contrast, high illumination)
- Automated refraction and keratometry
- Subjective sphero-cylindrical and best-vision sphere refraction plus distance visual acuity (high contrast, high illumination), monocular and binocular
- Ocular health assessment
- The participant will be fit with Clariti 1 Day
- Investigator refit ratings
- Eligibility will be confirmed and the participant continues to Visit 1A

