4.4.1.3 VISIT 1B: BASELINE PROCLEAR 1 DAY REVIEW

Visit 1B documents the baseline ProcLEAR 1 Day performance. It may occur: a) during Visit 1 for participants where their habitual ProcLEAR 1 Day lenses are of an optimal power, or b) after Visit 1A after the dispensed ProcLEAR 1 Day lenses have been used for at least the past 7 days. The following procedures will be conducted during this visit:

- Changes to health or medication*
- Monocular and binocular distance visual acuity (high contrast, high illumination)
- Fit assessment of ProcLEAR 1 Day
- 
- Remove contact lenses
- Ocular health assessment*
- Visual acuity with habitual spectacles (high contrast, high illumination)*
- Participant continues to Visit 2

*These procedures are not required if Visit 1B is concurrent to Visit 1.

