4.4.1.4 VISIT 2: DISPENSE CLARITI 1 DAY

Visit 2 occurs after Baseline Proclear 1 Day data has been collected (Visit 1B). At this visit, Clariti 1 Day will be dispensed. The following procedures will be conducted during this visit:

- Changes to health or medication*
- Ocular health assessment*
- Insert Clariti 1 Day
- Monocular and binocular distance visual acuity (high contrast, high illumination) with contact lenses
- Fit assessment of contact lenses
[REDACTED]
- Provide sufficient Clariti 1 Day to wear daily for at least 7 days (maximum 12 days)
[REDACTED]
- Participant advised to return for Visit 3 wearing Clariti 1 Day

*These procedures are not required if Visit 2 is concurrent to Visit 1, or Visit 1B.

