4.4.1.5 VISIT 3: REVIEW CLARITI 1 DAY

Visit 3 occurs after the participant has worn Clariti 1 Day for 7-12 days. Participants will attend this visit wearing Clariti 1 Day for at least 2 hours. The following procedures will be conducted at this visit:

- Changes to health or medication
- Collect at-home diaries
- Monocular and binocular distance visual acuity (high contrast, high illumination)
- Fit assessment of Clariti 1 Day lenses
[REDACTED]
[REDACTED]
[REDACTED]
- Remove contact lenses
- Ocular health assessment
- Participant continues to the Study Exit Visit

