4.5.11 BIOMICROSCOPY

A slit lamp biomicroscopy examination will be conducted to assess anterior segment ocular health. Ocular findings will be graded using the BHVI grading scale (0-4, 0.25 steps – unless otherwise stated):

- External adnexa anomalies (absent / present & describe)
- Hyperemia:

- Overall bulbar
- Overall limbal
- Corneal examination:
 - Scars or other corneal observations (absent / present & describe)
 - Infiltrates (absent / present & number, size, depth)
 - Sectoral corneal staining with fluorescein (type and extent [using CCLR 0-100 scale, 1 step] and depth [0-4, 1 step])
- Overall conjunctival staining and indentation (0-4, 0.5 steps)
- Palpebral conjunctiva:
 - Hyperemia
 - Roughness

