11 STATISTICAL ANALYSIS AND DATA MANAGEMENT

11.1 STATISTICAL ANALYSIS

All data will be analyzed by the CCLR at the University of Waterloo. Unmasked data analysis will be conducted using Statistica 12 and/or SPSS 24. Descriptive statistics will be provided on information regarding baseline variables (age, gender, refractive error distribution, etc.). For data completed on each eye individually (e.g. biomicroscopy), results of the right eye will be reported unless a difference between right eye and left eye is found. Table 4 lists the primary outcome variables and anticipated statistical procedures.

Table 4 : Statistical procedures

Variable	Analysis	Statistical test
Numeric rating scales Visual acuity Lens fitting Biomicroscopy (continuous variables)	Effect of lens type	Paired t-test Wilcoxon matched pairs test
Biomicroscopy (ordinal variables)	Effect of lens type	Friedman Wilcoxon matched pairs test
Subjective preference ratings Investigator refit agreement ratings	Preference of lens type	Binomial test

All data will be tested for normality of distribution using Shapiro-Wilk tests. The appropriate statistical test will be selected based on tests of normality. Statistical significance will be set at 5%, with no adjustments for multiple comparisons. In the event of missing data, individual data points will be excluded in the analysis and not extrapolated from the collected data.

A binomial test will be used to analyze the results for the count data of subjective preferences and investigator refit agreement ratings. The number of “no preference” (if featured on the scale) will be evenly distributed to the two options on the basis respondents would be equally likely to choose either.

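### On the concurrent-visit route for habitual Proclear wearers, the baseline slit-lamp grading follows a full refraction, whereas Clariti is graded directly after lens removal, so time off the lens is confounded with lens type in the supporting biomicroscopy comparison

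*Combined protocol and SAP*

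**What the plan says.** Section 4.4.1.1 sets out Visit 1 for habitual Proclear wearers with optimal power. The baseline review is embedded: "Visit 1B will be completed immediately (specifically: fit assessment and collection of subjective ratings for Proclear 1 Day". No slit-lamp examination is named in that embedded review. The lenses then come out, and three steps follow: acuity with spectacles, automated refraction with keratometry, and "Subjective sphero-cylindrical and best-vision sphere refraction plus distance visual acuity (high contrast, high illumination), monocular and binocular". The ocular health assessment comes next, before Clariti is fitted.

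Section 4.4.1.3 stars the Visit 1B ocular health assessment and adds: "These procedures are not required if Visit 1B is concurrent to Visit 1". Section 4.4.1.4 does the same for Visit 2: "These procedures are not required if Visit 2 is concurrent to Visit 1, or Visit 1B".

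For Clariti, Section 4.4.1.5 states: "Participants will attend this visit wearing Clariti 1 Day for at least 2 hours". After the in-lens measurements the lenses are removed, and the next listed step is "Ocular health assessment". A stand-alone Visit 1B, used for power-changed and other-lens participants, also puts the assessment directly after removal and before spectacle acuity.

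Section 4.5.11 grades bulbar, limbal and palpebral hyperaemia, corneal staining, and "Overall conjunctival staining and indentation (0-4, 0.5 steps" among others. Table 4 in Section 11.1 assigns paired or matched tests of lens type to the continuous biomicroscopy variables and to "Biomicroscopy (ordinal variables".

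**The concern.** The biomicroscopy analysis is a within-participant comparison, so it depends on both lenses being graded under the same conditions. On this route they are not: three procedures separate lens removal from grading for Proclear and none for Clariti. The difference runs the same way for everyone on the route, so a larger sample does not remove it. The affected participants belong to the group that Section 1 calls the primary target population.

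If lens-related signs fade after removal, Proclear is graded after some recovery and Clariti is not. A real improvement on Clariti could be hidden, or an apparent worsening reported. Table 4 also pools these participants with those graded directly after removal at both visits, and the plan has no time-since-removal field, adjustment or analysis by route.

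**Working it through.** **Order of steps, side by side**

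| Grading | Steps listed between lens removal and slit lamp |
|---|---|
| Proclear, optimal-power habitual wearer, visits concurrent (4.4.1.1) | spectacle acuity; auto-refraction and keratometry; subjective refraction with acuity |
| Proclear, stand-alone Visit 1B (4.4.1.3) | none |
| Clariti, Visit 3 (4.4.1.5) | none |

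The redacted lines in the Visit 3 list come before lens removal, so nothing hidden sits between removal and grading. With Visits 1B and 2 both concurrent, their own assessments are waived and the late Visit 1 grading is the only one after Proclear wear. If Visit 2 falls on another day, Section 4.4.1.4 requires a further assessment, and the plan does not say which grading is the Proclear comparator.

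**The plan's own figure.** Section 4.2.1 gives 67 participants for a 7-unit comfort difference at alpha 0.05 and power 0.8, without an SD. It cannot be reproduced independently. Solving the two-sided paired formula for the SD gives 7 × √67 / (1.960 + 0.842) ≈ 20.5 units. This concerns comfort, not biomicroscopy; only n = 67 is used below.

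**Illustration of size.** From the documents: n = 67 completing (4.2.2) and a 5% significance level without multiplicity adjustment (11.1), taken as two-sided. Assumed, because the documents give neither: a timing shift of b SDs of the paired difference, and a share f of participants on this route. The true lens effect is set to zero.

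- Mean shift over all participants: f × b.
- SD of the pooled differences: √(1 + f(1 − f)b²).
- Noncentrality: λ = f × b × √67 / √(1 + f(1 − f)b²), with √67 = 8.185.
- False-positive rate: probability that a noncentral t with 66 degrees of freedom falls beyond the two-sided 5% limits.

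| b | f | λ | False-positive rate |
|---|---|---|---|
| 0 | any | 0 | 5.0% |
| 0.2 | 25% | 0.05 × 8.185 / 1.004 = 0.41 | 6.9% |
| 0.2 | 50% | 0.10 × 8.185 / 1.005 = 0.81 | 12.6% |
| 0.2 | 100% | 0.20 × 8.185 = 1.64 | 36.5% |
| 0.5 | 25% | 0.125 × 8.185 / 1.023 = 1.00 | 16.7% |
| 0.5 | 50% | 0.25 × 8.185 / 1.031 = 1.99 | 49.9% |
| 0.5 | 100% | 0.50 × 8.185 = 4.09 | 98.1% |

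On an assumed SD of 0.5 grade, these shifts equal 0.10 and 0.25 grade. The calculation uses the paired t-test, one of the tests Table 4 lists for continuous biomicroscopy variables. For the rank-based tests it is a guide only.

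**The case against.** The strongest reply is that this is peripheral and unproven. The visible text of Section 2 names refit responses and lens fit as the primary outcomes, and Section 3 states the null hypothesis for fit alone. Fit is graded with the lenses in place for both products, so the order of later steps cannot affect it. Nothing in the documents says that any sign changes over the delay, and the delay itself is not given. Table 2 allows 1 hour for the whole of Visit 1, or 1.25 hours if both lenses are fitted, so time off the lens before grading is only part of that. All of this stands. It limits the importance of the point but does not remove the difference in order.

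It can also be said that refraction before slit lamp is a sensible screening order, used on all three Visit 1 routes, and that it keeps fluorescein away from refraction. That is a fair reason for the order at screening. It is weaker where the screening grading doubles as the lens baseline, and the protocol already accepts slit lamp before spectacle acuity at a stand-alone Visit 1B. The lists do not say that their order is binding; if it is not, the interval is simply uncontrolled.

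Finally, other limits would survive the fix. The study is open-label with a fixed sequence, and the 2-hour minimum wear at Visit 3 has no stated counterpart for Proclear. This too stands.

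A reader might go further and infer a false safety signal. The documents do not support that. The adverse-event definitions in Section 7 rest on clinical findings or, for two codes, on a two-grade change from baseline; a mean shift of a fraction of a grade would not by itself meet them.

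**Conclusion.** The point holds as a design weakness in a supporting comparison. For optimal-power habitual Proclear wearers with concurrent Visits 1, 1B and 2, time off the lens differs systematically between products. If signs fade after removal, the bias runs against Clariti. The order of steps is documented; fading, its rate and the share of participants affected are not.

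The range of about 7% to 98% therefore shows that the plan cannot tell a trivial distortion from a serious one. It is not an estimate. The upper end needs every participant to be on this route and a shift of 0.5 SD, although Sections 1 and 4.1.1 expressly provide for other-lens wearers and power changes.

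A reader might infer that the trial's main conclusion is at risk, since Section 11.1 introduces Table 4 as listing the primary outcome variables. The visible list in Section 2 does not include biomicroscopy, and lens fit is unaffected, so that inference does not follow. The change is worth making because it is cheap and removes a one-directional difference; the study's main result does not depend on it.

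**What to change.** In the optimal-power list of Section 4.4.1.1, and on the screening form, move the ocular health assessment to directly after lens removal, as at Visit 3 and at a stand-alone Visit 1B. If fluorescein before refraction is unwanted, grade at least the white-light items at that point (hyperaemia, palpebral roughness, and indentation where visible) and leave the fluorescein step after refraction. In that case record minutes since lens removal at Visit 1 and Visit 3, and report staining with that caveat.

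State in Section 11.1 that this Visit 1 grading is the Proclear comparator for this route, including when Visit 2 is on a separate day.

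Cost: one reordered list, a form change and one sentence in the analysis section, with no extra visits and no change in sample size. Either refraction then follows the slit lamp, or the slit lamp is used twice at that visit. The limits of the open-label, fixed-sequence design remain.

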4.4.1.2 VISIT 1A: DISPENSE PROCLEAR 1 DAY

Visit 1A only occurs for participants that: a) required an amendment to the power of their habitual ProcLEAR 1 Day lenses or b) are habitual wearers of other lenses. This visit may be scheduled to be on the same day as Visit 1. The following procedures will be conducted during this visit:

- Changes to health or medication*
- Ocular health assessment*
- Dispense ProcLEAR 1 Day
- Monocular and binocular distance visual acuity (high contrast, high illumination) with contact lenses
- Fit assessment of contact lenses
- Provide sufficient ProcLEAR 1 Day to wear daily for at least 7 days
- Participant advised to return for Visit 1B wearing ProcLEAR 1 Day

*These procedures are not required if Visit 1A is concurrent to Visit 1.

4.4.1.3 VISIT 1B: BASELINE PROCLEAR 1 DAY REVIEW

Visit 1B documents the baseline ProcLEAR 1 Day performance. It may occur: a) during Visit 1 for participants where their habitual ProcLEAR 1 Day lenses are of an optimal power, or b) after Visit 1A after the dispensed ProcLEAR 1 Day lenses have been used for at least the past 7 days. The following procedures will be conducted during this visit:

- Changes to health or medication*
- Monocular and binocular distance visual acuity (high contrast, high illumination)
- Fit assessment of ProcLEAR 1 Day
- 
- Remove contact lenses
- Ocular health assessment*
- Visual acuity with habitual spectacles (high contrast, high illumination)*
- Participant continues to Visit 2

*These procedures are not required if Visit 1B is concurrent to Visit 1.

4.4.1.4 VISIT 2: DISPENSE CLARITI 1 DAY

Visit 2 occurs after Baseline Proclear 1 Day data has been collected (Visit 1B). At this visit, Clariti 1 Day will be dispensed. The following procedures will be conducted during this visit:

- Changes to health or medication*
- Ocular health assessment*
- Insert Clariti 1 Day
- Monocular and binocular distance visual acuity (high contrast, high illumination) with contact lenses
- Fit assessment of contact lenses
[REDACTED]
- Provide sufficient Clariti 1 Day to wear daily for at least 7 days (maximum 12 days)
[REDACTED]
- Participant advised to return for Visit 3 wearing Clariti 1 Day

*These procedures are not required if Visit 2 is concurrent to Visit 1, or Visit 1B.

4.4.1.5 VISIT 3: REVIEW CLARITI 1 DAY

Visit 3 occurs after the participant has worn Clariti 1 Day for 7-12 days. Participants will attend this visit wearing Clariti 1 Day for at least 2 hours. The following procedures will be conducted at this visit:

- Changes to health or medication
- Collect at-home diaries
- Monocular and binocular distance visual acuity (high contrast, high illumination)
- Fit assessment of Clariti 1 Day lenses
[REDACTED]
[REDACTED]
[REDACTED]
- Remove contact lenses
- Ocular health assessment
- Participant continues to the Study Exit Visit

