3 HYPOTHESIS

The null hypothesis for this study is that there is no difference in lens fit performance between Proclear 1 Day (omafilcon A) and Clariti 1 Day (somofilcon A) lenses.

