4.5.6 STUDY LENS FIT ASSESSMENT

The study lenses will be assessed for the following during the lens fit assessment at Visit 1B and Visit 3:

- Lens wettability (0-4, 0.25 steps, where 0 = excellent, 4 = very poor)
- Lens deposition (0-4, 0.5 steps, where 0 = no deposits, 4 = deposits \geq 0.5mm or film > 75% of surface)

- Decentration (optimum / decentration acceptable / decentration unacceptable)
- Corneal coverage in primary gaze (yes / no)
- Post-blink movement (0-4, 1 step, where 0 = insufficient, unacceptable movement, 2 = optimal movement, 4 = excessive, unacceptable movement)
- Tightness on push-up (0-100%, 1% steps, where 0% = falls from the cornea, 50% = optimum, 100% = no movement)
- Overall fit acceptance (0-4, 1 step, where 0 = should not be worn, 4 = perfect), providing a reason if Grade 2 or less

[Redacted]

[Redacted]

[Redacted]

[Redacted]

[Redacted]

[Redacted]

[Redacted]

[Redacted]

[REDACTED]

[REDACTED]

[REDACTED]

[REDACTED]

[REDACTED]

[REDACTED]

[REDACTED]

[REDACTED]

[REDACTED]

[REDACTED]

[REDACTED]

[REDACTED]

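### The lens-fit comparison sets a same-day minimum wear time for Clariti but no comparable one for Proclear, so lens type can be confounded with hours on eye

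*Combined protocol and SAP*

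**What the plan says.** Section 2 lists lens fit and the investigator's responses to refit questions as the primary outcomes. Section 3 states the null hypothesis as "there is no difference in lens fit performance between Proclear 1 Day (omafilcon A) and Clariti 1 Day (somofilcon A) lenses".

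Section 4.5.6 fixes when fit is graded: "The study lenses will be assessed for the following during the lens fit assessment at Visit 1B and Visit 3". The items include wettability (0 to 4 in steps of 0.25) and deposition. Table 4 in section 11.1 tests lens fitting for an effect of lens type, by paired t-test or Wilcoxon matched pairs test, but does not say which visits are paired. Table 3 marks a fit assessment at five visits (1, 1A, 1B, 2 and 3).

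On wear before the assessment:

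- **Clariti, Visit 3 (section 4.4.1.5):** "Participants will attend this visit wearing Clariti 1 Day for at least 2 hours".
- **Proclear, habitual wearers (section 4.4.1.1):** "Participants that habitually wear Proclear 1 Day lenses will attend Visit 1 wearing their own Proclear 1 Day lenses". If the power is optimal, "Visit 1B will be completed immediately".
- **Proclear, dispensed at Visit 1A (sections 4.4.1.2 and 4.4.1.3):** "Participant advised to return for Visit 1B wearing ProcLEAR 1 Day", once the "lenses have been used for at least the past 7 days".
- **Both lenses, at fitting (section 4.5.5):** at least 2 minutes of settling. Table 3 schedules this fitting at Visit 1.

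On the refit rating, section 4.4.1.1 lists it at Visit 1 for habitual wearers of other lenses, ahead of Visit 1A, where Proclear is first dispensed to them. The objective in section 2 concerns people who are habitual or adapted Proclear wearers.

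**The concern.** The comparison that tests the stated hypothesis has a same-day wear rule on one side only. A Proclear assessment made minutes after insertion would comply with the readable text; a Clariti assessment made at the same point would not. Wettability and deposition are the items most likely to change over a day of wear, so a difference in hours on eye could be reported as a difference between lenses.

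The design offers little other protection. There is no randomization (section 4.1.2) and no masking (section 4.1.3), Proclear is always assessed before Clariti, and each lens contributes one assessment to the comparison. Unless hours worn are recorded, the analysis cannot separate the two explanations.

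A smaller matter concerns the other primary outcome. For habitual wearers of other lenses, the only visible refit rating is made before they have adapted to Proclear. Pooled with ratings of established Proclear wearers, it does not cleanly address the population named in the objective.

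**Working it through.** **Reading the text.** Set side by side, the Proclear requirements concern days of use and arriving with the lens in; only the Clariti requirement concerns hours on the day. The 2-minute settling time covers both lenses but belongs to the fitting procedure. Section 4.5.6 does not repeat it, and it is far shorter than 2 hours. Section 5 monitors time windows, but only those the protocol describes, and none is visible for same-day Proclear wear. Pairing Visit 1B with Visit 3 is an inference from section 4.5.6.

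**The plan's own figure.** Section 4.2.1 gives 67 participants for a 7-unit comfort difference at alpha 0.05 and power 0.8. No SD is stated, so 67 cannot be reproduced, only back-solved: a two-sided paired t-test implies an SD of paired differences of about 20.2 units. That figure concerns comfort, so only n = 67 is carried forward.

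**Illustration.** The documents give neither a paired SD for wettability nor a wear-time effect, so both are assumed.

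- n = 67 pairs (target completers, section 4.2.2), 66 degrees of freedom, two-sided 5%, critical t = 1.997.
- Assumed artefact *a*: half a wettability step (0.125) or one step (0.25).
- Assumed SD of paired differences *s*: 0.5, 0.75 or 1.0.
- Assumed share affected *f*: 100% or 25%.
- No true lens difference.

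The mean shift is *f* × *a*. The noncentrality is (*f* × *a* / *s*) × √67, and the probability of a false lens difference is the chance that the noncentral t falls outside ±1.997.

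Two worked cases with *a* = 0.125 and *s* = 0.5:

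- *f* = 1: 0.125 / 0.5 = 0.25; 0.25 × 8.185 = 2.046; probability 0.523.
- *f* = 0.25: 0.03125 / 0.5 = 0.0625; 0.0625 × 8.185 = 0.512; probability 0.080.

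| Artefact | Share affected | s = 0.5 | s = 0.75 | s = 1.0 |
|---|---|---|---|---|
| 0.125 | 100% | 52% | 27% | 17% |
| 0.125 | 25% | 8% | 6% | 6% |
| 0.25 | 100% | 98% | 77% | 52% |
| 0.25 | 25% | 17% | 10% | 8% |

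With no artefact the rate is the nominal 5%. With 10% affected it lies between 5% and 7% in all six combinations. In the partial cases *s* is held at its assumed value; adding the extra spread from mixing affected and unaffected participants does not change the rounded figures. For scale, a shift of 0.347 SD is detected with 80% power at n = 67. The Wilcoxon alternative was not computed.

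**The case against.** Much can be said for the plan. Eligible participants wear lenses at least 10 hours a day on at least 5 days a week (section 4.2.3), and those assessed in Proclear arrive wearing it, so many will have worn it for some hours. At a concurrent Visit 1, history, acuity and over-refraction are listed before the fit assessment. The settling time means it would be wrong to say that Proclear has no same-day time at all. Section 4.5.6 is followed by redacted text, Visit 1B has an empty bullet, and the forms in Appendices 4, 6 and 7 are not visible; any of these could hold a wear instruction or an hours-worn field. Wettability is one of seven fit items, several of which are categorical or coarse. Finally, a minimum is not a window: with equal minimums, one lens could still be graded at 2 hours and the other at 10.

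These points limit the size of the concern and shape the remedy. They do not remove the asymmetry in the readable text, because usual behaviour is neither required nor visibly recorded.

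On the refit rating, the rater is the investigator, the question wording is not visible, and Visits 2 and 3 contain redacted lines that could hold a later rating. Section 4.1.1 also explains the screening fit of Clariti as a check that participants can wear it. A reader might infer that this primary outcome is never collected after adaptation. The documents do not establish that.

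**Conclusion.** The concern holds in a limited form. As written, the plan allows unequal same-day wear in the comparison that tests its null hypothesis, so lens type can be confounded with hours on eye.

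A reader might take the larger percentages as this trial's false-positive risk, or conclude that the comparison favours a particular lens. Neither is supported. Those percentages require every participant to carry the full artefact; if a quarter do, the range across both artefact sizes falls to 6% to 17%. The artefact, SD and share affected are all assumptions, and the direction cannot be determined from the documents.

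The point is worth correcting because it touches a primary outcome and costs little to correct. Confidence is medium, given the redactions and unseen forms. The refit-rating point is secondary and supports only a change in reporting.

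**What to change.** 1. Apply to the Visit 1B fit assessment, including when it is concurrent with Visit 1, the same minimum same-day wear as at Visit 3.
2. Record hours worn at both visits if the forms do not already do so. Because an equal minimum does not equalise wear time, this record is what allows a remaining difference in hours to be examined.
3. State in section 11.1 that the lens-fit test pairs Visit 1B with Visit 3.
4. Report the investigator refit ratings by habitual lens type as well as pooled.

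The first two items cost one appointment instruction and possibly one form field; some habitual Proclear wearers may need a later appointment or a short wait. The third is one sentence. The fourth uses data already collected, but the subgroups will be smaller and their size is not planned. A second refit rating at Visit 2 is not recommended here: in an open-label study the first rating could influence it, and it would be missing for anyone lost during the Proclear run-in.
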